12.1.2 Descriptive Statistics

All endpoints will be summarized with descriptive statistics including number of subjects (n), number and percent of subjects with missing data, arithmetic means and standard deviations (mean and SD), median, minimum and maximum. For log normally distributed endpoints geometric mean, geometric CV will also be presented (note: categorical variables will be summarized by frequency statistics [number and percentage]). For endpoints relating to sampling times (e.g. t_{max}) only median and range will be presented. All analyses and summaries will be performed separately for fixed puffing and *ad libitum* use, with the exception of AEs.

12.1.3 Handling of Missing Values and of Values outside the Detection Limits

In general, missing data will not be imputed in this study, due to the nature of the measurements and the short periods of exposure and use. However, for questionnaire data total scores and domain or subscale scores may use a certain degree of imputation by averaging across individual item scores. Further details will be provided in the SAP.

In general, for the estimation of PK parameters, values below the lower limit of quantification (LLOQ) will be treated as missing and will be ignored in the PK evaluation.

12.2 Determination of Sample Size and Power Consideration

The sample size is empirically based, as there is no prior information on which to base the sample size and there is no consideration for statistical hypothesis. A sample of 12 subjects is targeted for the analysis of this study to optimize the precision about the mean and variance for the study objectives. Therefore 16 subjects will be randomized to allow for up to 25% of subjects to have at least one product exposure period with incomplete data.

12.3 Analysis Populations

All analyses will be based on actual product exposure. All endpoints (other than safety) will be analyzed using the nicotine PK analysis sets. Safety will be analyzed using the safety population.

12.3.1 Pharmacokinetic Population

The nicotine exposure analysis sets consist of all randomized subjects who give informed consent, completed at least one of the single uses of P4M3, and for whom at least one nicotine exposure parameter can be derived. Only subjects without major protocol deviations will be included in the nicotine exposure analysis sets.

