4 INVESTIGATIONAL PLAN

4.1 Overall Study Design and Plan

This is a single-center, open-label, concentration-ranging study to evaluate the nicotine PK profile and PD effects in healthy White adult experienced users of closed tank/cartridge e-cigarettes using four different variants of P4M3 or their own e-cigarettes.

A Screening Visit, including a demonstration of the P4M3 by the investigational site personnel, will be conducted within 3 weeks (Day -23 to Day -3) prior to Admission (Day -2) (see [Figure 1](#)).

On Day -2, subjects will be admitted to the investigational site at Admission. Subjects should have been fasting for at least 12 hours prior to Admission. After confirmation of subjects' eligibility, subjects will be enrolled in the study and have a debriefing on P4M3 followed by a product test with P4M3-1.7% *ad libitum* for a maximum of 10 minutes. After the product test, subjects not willing and/or not ready to use (e.g., intolerance) P4M3 will be discontinued and may be replaced. Subjects willing to continue will enter their confinement period of 6 days, from Day -2 to Day 5. Following the product test, subjects will be required to abstain from any nicotine/tobacco containing product use for at least 10 hours until the first product use on Day -1.

On Day -1 to Day 4, subjects will use either their own closed tank/cartridge e-cigarette/e-liquid or one P4M3 variant with two different regimens as described in [Figure 1](#):

- a fixed puffing regimen comprising of 12 puffs in total at a rate of one puff every 30 seconds (± 5 seconds) with HPT recording in the morning.
- *ad libitum* use for 60 minutes (± 5 minutes) with HPT recording in the afternoon

The start of product use of subjects' own e-cigarette and P4M3 variant (first puff) for fixed puffing and for the 60 minutes (± 5 minutes) *ad libitum* use will be defined as T0. T0 should be at approximately the same time (± 30 minutes) for fixed puffing in the morning and for *ad libitum* use in the afternoon for subjects' own e-cigarette on Day -1 (Baseline) and for P4M3 variants on Days 1 to 4. T0 for 60 minutes *ad libitum* use should be at least 10 hours after T0 for fixed puffing. There will be a washout of at least 10 hours following each *ad libitum* product use with respect to the subsequent fixed puffing regimen in the next morning to allow adequate background correction of the fixed puffing regimen-related nicotine plasma concentrations.

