5.1.3 Discontinuation of Subjects from the Study

Subjects will be informed that they are free to withdraw from the study at any time. Subjects should be questioned for the reason of premature withdrawal, although they are not obliged to disclose it. This needs to be fully documented in source documents and reported in the CRF.

When a subject is discontinued (withdraws or is discontinued) from the study, the early termination procedure planned ([Section 9](#)) must be performed as soon as possible after the time of discontinuation unless subject withdrew the informed consent to do so. After the time of discontinuation, the subject will enter into a 7-day passive safety FU. Subjects withdrawn or discontinued from the study cannot re-enter the study.

Subjects must be discontinued from the study for any of the following reasons:

- Withdrawal of informed consent.
- Any AE or condition (including clinically relevant changes in a laboratory parameter) at the discretion of the Investigator.
- Positive pregnancy testing (no invasive procedures including the drawing of blood must be performed after detection of pregnancy, see [Section 8.5](#)).
- Female subjects starting contraception or hormone replacement therapy containing estrogens during the study.
- The use of any nicotine/tobacco product which is different from the assigned IP.
- The Sponsor or Investigator terminates the study.
- Discontinuation is considered to be in the best interest of the subject or the other subjects.

Subjects may be discontinued from the study for any of the following reasons:

- Lost to follow-up.
- Non-authorized concomitant medication as defined in the context of this study (in general, any concomitant medication should be discussed with the Contract Research Organization [CRO] Medical Monitor on an ongoing basis).
- Non-compliance to the study procedures.

Subjects discontinued after randomization will not be replaced and will not be allowed to re-enter. All withdrawals and discontinuations have to be documented properly in the CRF.

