11.1.2 Protocol Deviations

Protocol deviations are defined as those deviations from any procedure as defined in this document, including but not limited to, as any violation of inclusion/exclusion criteria, use of any nicotine or tobacco-containing product other than the assigned product during each of the exposure period, use of any nicotine tobacco-containing product during wash-out periods, assessments not performed or performed outside the scheduled time windows, or use of estrogen or other drugs that are known to affect CYP2A6 activity.

All protocol deviations will be documented appropriately in an approved format.

Information from the source documents will represent the primary source of protocol deviations. Information following site monitoring and other manual reviews will be documented in the site visit reports, follow-up letters, audit documentation, or other manual review and will be recorded and tracked in an approved format. Telecommunications and other verbal communications regarding deviations will be considered and handled as important communication, documented and tracked as protocol deviations, as necessary.

Data and information contained in this document are considered to constitute trade secrets and confidential commercial information, and the legal protections provided to such trade secrets and confidential information are hereby claimed under the applicable provisions of US law. No part of this document may be publicly disclosed without the written consent of PMI.

Individual entries for protocol deviations that are recorded following site monitoring and other manual reviews, will be reviewed against the individual data points in the CRF database but will not be formally reconciled with the CRF database (e.g., their description or occurrence date). The overall procedure for managing protocol deviations are described in the SOPs of the CRO Data Management Team. All deviations will be reviewed periodically, as determined at study start, to identify trends to improve monitoring and/or potential impact on the statistical analysis.

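### Section 12.3.1 drops a whole subject from the nicotine analysis sets for a major deviation in a single session, an avoidable loss of precision in a 16-subject trial

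*Protocol*

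**What the plan says.** Section 12.3.1 sets two conditions for the nicotine exposure analysis sets. The first is generous: a randomized, consenting subject qualifies who "completed at least one of the single uses of P4M3, and for whom at least one nicotine exposure parameter can be derived". The second is restrictive: "Only subjects without major protocol deviations will be included in the nicotine exposure analysis sets". It is worded by subject, and no section limits it to the session, day or regimen in which the deviation occurred.

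Section 12.3 says that all endpoints other than safety are analysed on these sets. The exclusion therefore also reaches craving, the questionnaires and puffing topography, although the pharmacodynamic population in section 12.3.2 carries no such condition.

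On the number of sessions, section 4.1 says: "On Day -1 to Day 4, subjects will use either their own closed tank/cartridge e-cigarette/e-liquid or one P4M3 variant with two different regimens". On numbers of subjects, section 12.2 says: "A sample of 12 subjects is targeted for the analysis of this study"; and "16 subjects will be randomized to allow for up to 25% of subjects to have at least one product exposure period with incomplete data". Section 5.1.3 rules out replacement after randomization.

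Section 11.1.2 lists kinds of deviation, some tied to one occasion (for example "assessments not performed or performed outside the scheduled time windows"), but does not say which are major.

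**The concern.** In a within-subject study the session is the natural unit of data validity. A deviation that spoils one session need not spoil the others. Under section 12.3.1 as worded, a major deviation confined to, say, the Day 2 morning session also removes that subject's own e-cigarette reference from Day -1 and the sessions on the other days.

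The product comparisons do not need this. Sections 12.5.2 and 12.6.2 fit product as a fixed effect and subject as a random effect, so a subject with some sessions missing still contributes. The lactic acid comparison in section 12.6.2 is the exception: it treats subjects as fixed, so a subject informs it only with both 1.7% sessions. Even there, a deviation confined to another day is no reason to drop the pair.

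At stake is the width of the 90% confidence intervals for the variant to own e-cigarette ratios, in a trial with 16 subjects and no replacement.

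**Working it through.** **1. The plan's own figure.** Section 12.2: 12 / (1 − 0.25) = 16. This reproduces. The target of 12 is empirical and no hypothesis is tested, so there is no power figure to check.

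**2. Sessions.** Day -1 and Days 1 to 4 are 5 days; with 2 regimens, 5 × 2 = 10 sessions per subject and 16 × 10 = 160 in all. One major deviation under the written rule removes 10 of 160 sessions (6.25%) and takes N from 16 to 15. Session-level exclusion removes 1 of 160.

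**3. Two readings of the rule.** Section 12.3.1 speaks of sets in the plural, and section 12.1.2 has the two regimens analysed separately. The exclusion may act on one pooled set (m = 10 sessions) or on one set per regimen (m = 5). Both are shown.

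**4. Assumption.** The protocol gives no deviation rate. Let q be the chance of a major deviation in one session, independent across sessions, with q = 1, 2 and 5%.

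**5. Formulas.**
- Share of subjects excluded: 1 − (1 − q)^m. Expected number kept: 16(1 − q)^m.
- Session-level exclusion: a paired contrast needs two valid sessions, so the expected number of pairs is 16(1 − q)².
- The half-width of the 90% interval for a paired log-ratio is proportional to h(n) = t(0.95, n − 1)/√n. The standard deviation cancels in the ratio of two half-widths. h is evaluated at the expected n.

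**6. One case in full (q = 2%, pooled).** Kept: 16 × 0.98^10 = 13.1. Session-level pairs: 16 × 0.98² = 15.4. h(13.07) = 1.781/√13.07 = 0.493; h(15.37) = 1.758/√15.37 = 0.448. Ratio 1.10, so the interval is about 10% wider.

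**7. Results.**

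| q | Excluded, pooled | Kept, pooled | Excluded, per regimen | Kept, per regimen | Pairs, session-level | CI wider, pooled | CI wider, per regimen |
|---|---|---|---|---|---|---|---|
| 1% | 9.6% | 14.5 | 4.9% | 15.2 | 15.7 | 5% | 2% |
| 2% | 18.3% | 13.1 | 9.6% | 14.5 | 15.4 | 10% | 4% |
| 5% | 40.1% | 9.6 | 22.6% | 12.4 | 14.4 | 28% | 9% |

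The exact binomial probability of keeping fewer than 12 subjects at q = 1, 2 and 5% is 1.4, 15 and 84% (pooled), or 0.1, 1.4 and 29% (per regimen). Under session-level exclusion, the probability that a given product and regimen has fewer than 12 subjects is below 0.1% throughout.

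**8. Where the 25% allowance runs out.** Solving 1 − (1 − q)^m = 0.25 gives q = 1 − 0.75^(1/10) = 2.8% (pooled) or 1 − 0.75^(1/5) = 5.6% (per regimen).

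**The case against.** **How often the rule applies is unknown.** It covers only major deviations. Section 11.1.2 lists deviations of all kinds and grades none, so a reader might infer that a late sample removes a subject. The protocol does not say that: section 12.6.2 uses actual sampling times and section 12.1.3 leaves missing values unimputed. Defining major is properly left to the SAP. Subjects are confined, supervised during P4M3 use and given product use by use, so a 5% rate of major deviations per session has no support in the document. Clustering within subjects would also remove fewer subjects than independence predicts. This stands; the table shows sensitivity and is not a forecast.

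**Section 12.2 is not contradicted.** A reader might see a conflict between the subject-level rule and the allowance "to allow for up to 25% of subjects to have at least one product exposure period with incomplete data". Incomplete data are not said to be a major deviation, and the first condition of section 12.3.1 keeps incomplete subjects in. The two sections concern different events.

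**Bias is not shown.** Because 3% and 4% come on Days 3 and 4 for everyone, a reader might infer that removal is driven by the stronger variants. But the foreseeable reaction, using less or stopping, is expressly allowed in sections 6.3 and 6.3.5 and is nowhere called a deviation. The selection argument remains conjecture.

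**Sessions are not fully separable.** Section 4.2 accepts incomplete washout, with a terminal half-life of 17 hours, and section 12.1.1 corrects sessions with an elimination rate estimated from Day 5 samples. Unassigned nicotine use late in the stay could thus spoil the correction of earlier sessions, and removing all of a subject's corrected data may then be right. This stands and shapes the fix.

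What remains is that the protocol, not the SAP, has fixed the unit of exclusion, and it is coarser than the analysis needs.

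**Conclusion.** The point holds as a minor one. As worded, section 12.3.1 discards valid sessions along with affected ones, and section 12.3 spreads this to all non-safety endpoints. A single exclusion costs little: going from 16 to 15 subjects widens a paired 90% interval by about 4%, and the allowance covers four subjects. At assumed rates of 1 to 2% per session, the rule widens intervals by 5 to 10% (pooled) or 2 to 4% (per regimen) relative to session-level exclusion, and the expected number stays above 12. At 5% the widening is 28% or 9%, and only the pooled reading falls below 12.

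These sizes rest on independent deviations, equal rates across sessions and a simple paired contrast. Within-subject clustering would make the loss smaller. The case is one of avoidable imprecision in a small trial; no estimate or conclusion is shown to be wrong.

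**What to change.** Reword the second condition of section 12.3.1 so that a major deviation excludes the session or sessions whose data it affects, and the subject's other sessions stay in. Say that affected sessions include:

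- the session in which the deviation occurred;
- later sessions affected through carry-over;
- sessions whose background correction relies on a Day 5 elimination rate that the deviation has made invalid.

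Exclude the whole subject only where all sessions are affected, for example by an eligibility violation. State whether there is one set or one per regimen.

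Classify deviations before the plasma nicotine data are analysed and reviewed by the sponsor under section 12.8, so that exclusions are settled without sight of the concentrations.

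The cost is a few lines of text and a session-by-session classification at a data review that takes place anyway. Numbers of subjects will then differ slightly between products and regimens, and tables should show n for each.

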12.3.2 Pharmacodynamic Population

The subjective measures analysis sets will include all subjects who used an IP and have pre-use and at least one post-use (Adapted mCEQ, VAS for craving, or SQ) data.

Data and information contained in this document are considered to constitute trade secrets and confidential commercial information, and the legal protections provided to such trade secrets and confidential information are hereby claimed under the applicable provisions of US law. No part of this document may be publicly disclosed without the written consent of PMI.

12.3.3 Safety Population

The safety set population, consists of all the subjects who give informed consent and have at least one exposure to P4M3 (including the product test at Admission [Day -2]).

12.4 Demographics and Baseline Characteristics

Demographic and other baseline characteristics will be reported for the safety population. Appropriate summary statistics will be provided.

12.5 Primary Objectives and Endpoints

12.5.1 Primary Endpoint Analysis Variables

Nicotine exposure parameters for *ad libitum* use will be derived from plasma nicotine concentration versus time data using a non-compartmental technique. In particular:

cC_{peak}	Background-corrected peak plasma nicotine concentration
t_{peak}	Time to peak plasma nicotine concentration during ad libitum use, t_{peak} will be reported as long as there is at least one quantifiable concentration post-exposure
cC_{trough}	Background-corrected trough plasma nicotine concentration
cC_{average}	Background-corrected average of plasma nicotine concentration between 0 to 1 hour
$cAUCb_{(0-4h)}$	Background-corrected area under the concentration-time curve that is above the corrected baseline from the start of ad libitum use to 4 hours.

Unadjusted PK parameters will also be presented. Additional plasma PK parameters may be derived and/or reported as appropriate.

12.5.2 Statistical Analysis

Endpoints for *ad libitum* use will be summarized as described in [Section 12.1.2](#).

Nicotine PK parameters will be derived from plasma nicotine versus time data using non-compartmental analysis. Plasma PK parameters will be summarized using descriptive statistics by product type (e.g., subjects' own e-cigarette or P4M3 variant), as appropriate.

For the 60-minute *ad libitum* uses, an ANOVA will be conducted on logarithmically transformed cC_{peak} , cC_{average} , and $cAUCb_{(0-4h)}$, as applicable. The model will be adjusted for sex and cC_{trough} value with product use as a fixed effect and subjects as a random effect. Wilcoxon signed-rank test will be used to compare t_{peak} between the test (P4M3 variant) and reference (subject's own) products.

Data and information contained in this document are considered to constitute trade secrets and confidential commercial information, and the legal protections provided to such trade secrets and confidential information are hereby claimed under the applicable provisions of US law. No part of this document may be publicly disclosed without the written consent of PMI.

The relationship between nicotine concentrations (with lactic acid only) and the nicotine PK parameters will be investigated graphically on an exploratory basis.

